5.3. Procedures for Maintaining and Breaking the Masking

Not applicable. As this is a non-dispensing trial, there is no foreseen situation in which the site would need to inform the subject of what contact lens they are wearing.

Clinical Study Protocol
Johnson & Johnson Vision Care, Inc.

6. STUDY INTERVENTION

6.1. Identity of Test Articles

The following contact lenses will be used in this study:

Table 1: Test Articles

	Acuvue® Oasys 1-Day for Astigmatism (Test)	Dailies® Total 1 for Astigmatism (Control)
Test Article Form	Soft toric contact lenses	
Description	Standard marketed lenses	
Manufacturer	Johnson & Johnson Vision Care, Inc.	Alcon Inc.
Packaging Form	Blister packaging with sterile packing solution	Blister packaging with sterile packing solution
Packaging Solution	Optimized Borate Buffer (OBB) solution	Packaged in solution containing wetting agents
Lens Material	senofilcon A	delefilcon A
Sphere Powers (DS)	Marketed SKUs (+4.00 to -6.00)	
Cylinder Powers (DC)	Marketed SKUs (0.75 to 2.50)	
Cylinder Axes (°)	Marketed SKUs	
Nominal Water Content (%)	41	Variable
Nominal Base Curve (mm)	8.5	8.6
Lens Diameter (mm)	14.3	14.5
Fiducial marks	6 and 12 o'clock fiducial lines	6 o'clock fiducial line
Dk	103	140
Wear Modality in Current Study	Daily wear	
Replacement Frequency in Current Study	Daily disposable	
Commercially available	Yes	Yes

The site will be acquiring and using the commercially available lots to match the prescription per subject.

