2.2. Endpoints

2.2.1. Efficacy Endpoints

Primary Efficacy Endpoint

1. Distance (6m) Visual Acuity

Clinical Study Protocol
Johnson & Johnson Vision Care, Inc.

The primary endpoint for this study will be distance visual acuity measured monocularly at 6 meters after lens fitting under high-luminance high contrast (HLHC) lighting conditions using the Eurolens computerized logMAR VA chart. The logMAR VA score is a continuous endpoint.

Other (Exploratory) Efficacy Endpoints

1. Lens orientation measured over time with an automated lens tracking system following intentional misalignment

Each study lens will be rotated in the temporal direction from its original position to its worst case orientation (90° from its settled position for the AO1DfA lens which has a bidirectional stabilization design, and 180° from its settled position for the DT1fA lens which has a unidirectional stabilization design), followed by video capture of the lens orientation over a 5-minute period. Lens orientation data (rotation error magnitude and direction relative to the 6 o'clock position, and rotation error magnitude and direction relative to original settled position) will be calculated at 5-second increments through the measurement period. Rotation error magnitude will be recorded in degrees (0 to 180), and rotation error direction will be recorded as base temporal or nasal. For the DT1fA lens type, recovery from 90° misalignment will also be determined from the timepoint that it reaches this position during the recovery from 180° of misalignment.

2. Lens orientation recorded with an automated lens tracking system following eye movements

Lens settled orientation (rotation error magnitude and direction relative to the 6 o'clock position) in primary gaze will be measured. Lens orientation will then be measured again after the subject has been asked to perform an eye movement in each of the eight cardinal directions of gaze. The difference in orientation (magnitude and direction) from before eye movement to after eye movement will be determined.

3. Settling Time following intentional misalignment

The time (in seconds) required for the study lenses to settle (defined as returning to within 5 degrees of initial settled position) after intentional misalignment will be recorded for each eye and lens during the assessment of the lens orientation recorded with an automated lens tracking system (Other efficacy endpoint 1). Settling time is a continuous endpoint.

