14.5. Statistical Analyses

Handling of Missing Data

All data summaries and statistical analysis will be conducted using the observed case data without multiple imputation. The count of missing data will be provided in each listing and table provided.

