14.6. Efficacy Analyses

All efficacy endpoints will be summarized for both the ITT and per-protocol population using observed case data without multiple imputation.

Primary Efficacy Endpoint

1. Distance Visual Acuity

Distance (6m) monocular HLHC logMAR visual acuity at fitting will be summarized and presented only descriptively by lens type and timepoint (if applicable). Summary statistics are described in section 14.1

Secondary Efficacy Endpoint

Not applicable.

Other Efficacy Endpoints

1. **Lens orientation measured over time with an automated lens tracking system following intentional misalignment** Data resulting from the processing of the videos of each subject eye (for each lens), will be summarized by parameter (rotation error magnitude [range: 0 to 180] and rotation error direction [base temporal or nasal]). The video processed will be approximately 5 minutes per eye per lens. The tracking software will measure the parameters at 5-second intervals, totaling for a plan of 60 observations per eye per lens. Rotation error magnitude is a continuous data point while the rotation error direction is nominal categorical data. Signed rotation will be derived based on rotation error magnitude and direction and will be included as part of the external data file detailed in section 15. Parameter data (rotation error magnitude, signed rotation, and rotation direction) reported (or derived) from the automated tracking system will be summarized as per section 14.1.

2. **Lens orientation recorded with an automated lens tracking system following eye movements**

In addition to collecting rotation error magnitude and direction following intentional misalignment, rotation error magnitude and direction will be recorded in each of the 8 cardinal gaze directions before and after eye movement. The signed rotation will be derived in the same manner as described above. Summaries will be provided for each parameter (rotation error magnitude, signed rotation, and rotation direction), timepoint (before and after eye movement) and gaze separately. Additional summaries will be provided for the 8 gazes combined.

The 8 cardinal gazes are:

- Up and to the right
- Upward
- Up and to the left
- Right
- Left
- Down and to the right
- Downward
- Down and to the left

3. **Settling Time following intentional misalignment**

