15. DATA HANDLING AND RECORD KEEPING/ARCHIVING

15.1. Electronic Case Report Form/Data Collection

The data for this study will be captured on electronic case report forms (eCRFs) using a Sitero EDC system. An authorized data originator will enter study data into the eCRFs using the EDC system. Data collected on equipment that is not captured in EDC will be formatted to the specification of the JJVC database manager and sent to JJVC for analysis.

External data sources for this study include: Video files and Excel data files for lens orientation analysis per subject. Each video recording will show a single eye and its surrounding eyelid area (see Appendix G for example) without having personally identifiable information in the image or the filename. The video files will be provided in a standard video format (eg. mpeg). Video files are processed using tracking software (Open Source Physics – OSP) to estimate the lens orientation over a 5-minute period of recovery from intentional misalignment from the settled position. The rotation error direction and magnitude relative to two reference positions (relative to 6 o'clock position, and relative to initial settled position) will be provided. The signed rotation will be derived using rotation error magnitude and direction. Data is planned to be provided at 5 second increments, but alternative increments may be found to be necessary once data collection commences.

Additionally, lens orientation (direction and magnitude of rotation error relative to 6 o'clock position, and relative to initial settled position) following eye movements in 8 directions of gaze will be provided in a separate Excel spreadsheet.

The clinical data will be recorded on dedicated eCRFs specifically designed to match the study procedures for each visit. Only specifically delegated staff can enter data on a CRF. Once completed, the eCRFs will be reviewed for accuracy and completeness and signed by the Investigator. The sponsor or sponsor's representatives will be authorized to gain access to the subject recordation for the purposes of monitoring and auditing the study.

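### If the upper lid hides the Control lens's single mark after its 180° turn, the observed-case rule drops the Control's largest rotation errors; the plan needs a code for hidden-mark readings

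*Combined protocol and SAP*

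**What the plan says.** - **Marks.** Section 6.1, Table 1, gives the fiducial row as "6 and 12 o'clock fiducial lines 6 o'clock fiducial line": two lines on the Test lens (AO1DfA), one on the Control (DT1fA).
- **Starting positions.** Section 2.2.1, exploratory endpoint 1, turns the Test lens "90° from its settled position for the AO1DfA lens which has a bidirectional stabilization design" and the Control "180° from its settled position for the DT1fA lens which has a unidirectional stabilization design". It also derives Control recovery from 90°, starting when the lens passes that angle on its way back from 180°.
- **Source of the readings.** Section 15.1: "Each video recording will show a single eye and its surrounding eyelid area". Section 14.6 says "The video processed will be approximately 5 minutes per eye per lens" and that the software will "measure the parameters at 5-second intervals, totaling for a plan of 60 observations per eye per lens". Magnitude is on a 0 to 180° scale.
- **Missing readings.** Section 14.5: "All data summaries and statistical analysis will be conducted using the observed case data without multiple imputation", and "The count of missing data will be provided in each listing and table provided". Section 14.6 repeats the observed-case rule for efficacy.

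The readable text does not name the lens feature that the tracker follows, does not say whether the lid is held during capture, and gives no rule for a frame in which the mark cannot be seen. Section 7, the orientation detail in Appendix D and the Appendix G image are not readable in the public copy. They may cover these points.

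**The concern.** The two lenses do not start with equally visible marks. A 90° turn leaves the Test's lines in the open part of the eye, at 3 and 9 o'clock. A 180° turn takes the Control's single line to the upper-lid position.

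A reading lost there is lost because of its own value: the error is close to 180°. Slow eyes lose more readings than fast ones. Missingness of this kind is informative, and an observed-case mean or median at an early time point then describes only the Control eyes that have already rotated far enough to be read. The Test lens has no matching mechanism at its starting position.

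At stake is the early part of the Control's rotation-magnitude summary. Section 1 names rotational performance of both lenses as something the study will evaluate, and section 14.2 rests the sample size on evaluating the tracking software. With a target of 10 eyes, one hidden eye matters.

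**Working it through.** **The plan's own figure.** 300 s ÷ 5 s = 60 readings per eye per lens, as section 14.6 states. With 10 eyes that is 600 readings per lens.

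**Geometry (assumed, not in the documents).** Let the mark lie r mm from the lens centre and the upper lid margin h mm above it. The mark is hidden within arccos(h/r) of 12 o'clock, so the largest readable error is 180° minus that angle.

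| r (mm) | h (mm) | hidden within | readable up to |
|---|---|---|---|
| 5.5 | 5 | 25° | 155° |
| 6.5 | 4 | 52° | 128° (central) |
| 7.0 | 3 | 65° | 115° |

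Marks at 3 and 9 o'clock are 90° from 12 o'clock, outside even the widest hidden arc (65°). The Test lens at its start, and the Control from 90° onward, are therefore readable in all three cases.

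**Early bias (assumed recovery).** Error m(t) = 180·exp(−t/τ), with τ lognormal across eyes, log-SD 0.7.

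- Median τ 30 s, limit 128°. At 10 s, 51% of Control eyes are hidden and the observed mean is 98° against a true 123° (25° too low). At 20 s, 17% are hidden and the means are 79° and 89° (10° too low).
- Median τ 60 s, limit 128°. At 20 s, 51% are hidden and the means are 98° and 123°.
- Median τ 30 s, limit 155°. The bias is about 13° at 5 s and 6° at 10 s.

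**Whole recording.** In the central case, mean hidden time is ln(180/128) × 30 × exp(0.7²/2) ≈ 13 s of 300 s. Counted on the 5-second grid, about 3.5% of readings are hidden, and the 5-minute mean is 16° against 21°.

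A simpler check gives every eye the same τ and hides readings within 30° to 60° of 12 o'clock:

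| τ and lag | true mean | observed mean | lost of 60 |
|---|---|---|---|
| 30 s, none | 16.5° | 12.3–14.2° | 1–2 |
| 60 s, none | 34.3° | 26.3–30.0° | 2–4 |
| 120 s, none | 64.7° | 50.2–57.7° | 4–9 |
| 60 s, after 60 s at 180° | 69.9° | 32.9–37.3° | 14–16 |

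**One eye that stays hidden.** Take nine eyes at τ = 60 s and one stuck at 178°, with readings within 45° of 12 o'clock hidden. The true mean is (9 × 34.3 + 178)/10 ≈ 48.7°. The observed mean is 28.1°, and 9 × 3 + 60 = 87 of 600 readings are lost.

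**Settling time.** With τ = 60 s and no lag, the error falls to 5° at 60 × ln(180/5) = 215 s, first met on the 5-second grid at 220 s. Dropping the early readings does not change that. Full and observed readings gave the same settling result in every lag scenario run. Only an eye whose mark does not reappear within 5 minutes loses its settling time to hiding.

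**The case against.** The strongest reply is that the premise is not in the documents. No readable section says that the tracker uses the printed line or that the lid covers it. The scribe mark in section 2.2.1 belongs to a different endpoint, the orientation at 1, 3 and 15 minutes. A 0 to 180° scale and 60 planned readings for both lenses suggest that the sponsor expects to read the Control throughout. Lid handling and frame-reading rules would normally sit in the procedures and appendices, which are withheld. All of this stands, and it is why the point is conditional.

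It also stands that the sizes rest on assumed geometry and recovery speed, that the largest whole-recording biases need an assumed lag or a stuck eye, and that the endpoint is exploratory, with no hypothesis test and no planned between-lens contrast.

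The missing-data count answers only part of the point. It would show that readings were lost. It would not separate a hidden mark from a blink or a tracking failure, and it would not correct the mean. Unreadable frames are indeed a feasibility finding in their own right, but only if they are coded as such.

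A reader might go further and infer that the plan will make the Control look better aligned than the Test lens. The documents do not support that. Any understatement is relative to the Control's own true values, and the full curves start at 180° and 90° by design, so they are not like-for-like in any case.

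**Conclusion.** The point holds as a conditional gap in the analysis rules. The documents establish the difference in marks, the 180° and 90° starts, and the observed-case rule. From these it follows that any reading lost because the Control's line is near 12 o'clock is one of its largest errors, and that observed-case summaries of early Control magnitude are then too low. Whether such readings are lost is not known from the readable text.

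The size is unknown. In the central assumed case it is tens of degrees at 10 to 20 s and about 5° over 5 minutes. Across the no-lag checks the 5-minute bias runs from about 2° (16.5 − 14.2) to 14° (64.7 − 50.2). A 60 s lag raises it to 33–37°. It is zero if no mark is hidden. Settling time is affected only for an eye whose mark never reappears, recovery from 90° is largely unaffected, and the primary endpoint is not affected.

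The change is worth making because it costs almost nothing and has no effect if no mark is hidden.

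**What to change.** In section 14.6, Other Efficacy Endpoint 1, and the external data file in section 15.1:

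1. State which lens feature the tracker follows. Code each 5-second reading as measured, mark hidden by the upper lid, or otherwise missing (blink, tracking failure).
2. Report the number of eyes in each code by lens and time point.
3. In the median and percentiles of rotation magnitude, rank hidden-mark readings as the largest values instead of dropping them. Where the median itself falls among hidden readings, as it would with 51% hidden, report it as above the readable range.
4. Keep the section 14.1 means, and label them observed-case only at any time point with hidden readings.
5. Base any side-by-side comparison of recovery on errors of 90° or less, which section 2.2.1 already derives for the Control.

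Do not enter a nominal 180° as the Control's value at time zero. It would replace a measurement with the target of a manual rotation, and 180° from the settled position need not be 180° from 6 o'clock, the plan's other reference.

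The cost is one extra spreadsheet code and slightly more complex early summaries, with no added subjects, visits or procedures. If the withheld procedures already deal with a hidden mark, a cross-reference to them can replace the definition in step 1.

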6.2. Ancillary Supplies/Products

The following solutions will be used in this study:

Table 2: Ancillary Supplies

	Non-Preserved Saline
Solution Name/Description	Astroplast Ultra Saline 20ml Pods or similar
Manufacturer	Wallace Cameron International Ltd
Preservative	None

[figure not shown]
The sites will be acquiring the ancillary supplies as needed for the study including lens cases or fluorescein strips.

6.3. Administration of Test Articles

[figure not shown]
Test articles will be dispensed to subjects meeting all eligibility requirements, for in-office wear only as part of the requirements set forth in this clinical protocol.

**Clinical Study Protocol
Johnson & Johnson Vision Care, Inc.**

[figure not shown]
Clinical Study Protocol
Johnson & Johnson Vision Care, Inc.

[figure not shown]
Clinical Study Protocol
Johnson & Johnson Vision Care, Inc.

[figure not shown]
Clinical Study Protocol
Johnson & Johnson Vision Care, Inc.

[figure not shown]
Clinical Study Protocol
Johnson & Johnson Vision Care, Inc.

[figure not shown]
Clinical Study Protocol
Johnson & Johnson Vision Care, Inc.

[figure not shown]
Clinical Study Protocol
Johnson & Johnson Vision Care, Inc.

Clinical Study Protocol
Johnson & Johnson Vision Care, Inc.

Clinical Study Protocol
Johnson & Johnson Vision Care, Inc.

Clinical Study Protocol
Johnson & Johnson Vision Care, Inc.

Clinical Study Protocol
Johnson & Johnson Vision Care, Inc.

[REDACTED]

8. SUBJECTS COMPLETION/WITHDRAWAL

8.1. Completion Criteria

Subjects are considered to have completed the study if they:

- provided informed consent.
- they are eligible.
- have not withdrawn/discontinued from the study for any reason described in section .
- completed all visits through the final visit (Visit 2).
- If all visits were completed but an additional visit is considered necessary for subject care, follow the requirements for unscheduled visits in section .

8.2. Withdrawal/Discontinuation from the Study

A subject will be withdrawn from the study for any of the following reasons:

- Subject withdrawal of consent.
- Subject not compliant to protocol
- Subject lost to follow-up.
- Subject no longer meets eligibility criteria (e.g. the subject becomes pregnant).
- Subject develops significant or serious adverse events necessitating discontinuation of study lens wear
- Subjects who have experienced a Corneal Infiltrative Event (CIE).
- Investigator's clinical judgment regarding the subject safety reasons (that it is in the best interest of the subject to stop treatment).
- Subject missed any study visits
- Subject not compliant with study lens wear schedule
- Subject not successfully dispensed due to lack of efficacy and safety including poor vision, poor comfort or unacceptable fit.

For discontinued subjects, the Investigator will:

- Complete the current visit (scheduled or unscheduled).
- Complete the Final Evaluation, indicating the reason that the subject was discontinued from the study.
- Record the spherocylindrical refraction with best corrected distance visual acuity.
- Collect used test article(s) (worn or brought to the visit) from the subject and discard them, unless otherwise stated in section 7.2.
- Collect all unused test article(s) from the subject.
- Make arrangements for subject care, if needed, due to their study participation

Additional subjects may be enrolled if a subject discontinues from the study prematurely.

In cases where a subject is lost to follow-up, every possible effort must be made to contact the subject and determine the reason for discontinuation/withdrawal. The measures taken to follow up must be documented including two written attempts and a certified letter (or equivalent) as the final attempt.

Clinical Study Protocol
Johnson & Johnson Vision Care, Inc.

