Objectives	
Primary Objective: The primary objective of this study is to measure the monocular distance (6m) logMAR visual acuity with each study lens (Test lens and Control lens) after lens fitting.
 
Other (Exploratory) Objectives: The exploratory objectives of this study include changes in lens orientation after settling and over time with an automated lens tracking system; VAS scores after lens fitting for vision, comfort and handling; and lens orientation at 1, 3, and 15-minutes following insertion. Adverse events and slit lamp findings will also be monitored and collected.

Study Endpoints	
Primary Efficacy Endpoint:
 
 1. Distance Visual Acuity 
Other (Exploratory) Efficacy Endpoints:
 
 1. Lens orientation measured over time with an automated lens tracking system following intentional misalignment 2. Lens orientation recorded with an automated lens tracking system following eye movements 3. Settling Time following intentional misalignment 4. Toric Lens orientation at 1-, 3-, and 15-minutes following insertion 5. Subjective Vision, Comfort and Handling Scores approximately 15-minutes after lens insertion 
Other Safety Endpoints:
 
 1. Adverse Events (AEs) 2. Slit Lamp Findings (SLFs)

Clinical Study Protocol
Johnson & Johnson Vision Care, Inc.

Study Design	
This will be a single site, 2-visit, randomized, controlled, single-masked, non-dispensing, bilateral wear, 2×2 cross-over study. Each subject will be randomly assigned to one of two wear sequences. There will be a washout period of 1-10 days in between the visits.
 
There will be a total of 2 visits:
 
Visit 1: Screening, baseline evaluation and lens fit #1
 
Visit 2: Continuance, lens fit #2, Exit evaluation
 
See the flow chart at the end of the synopsis table for the schematic of the study visits and procedures of main observations () .

Sample Size	
This study will have an enrollment target of approximately 7 subjects, with a target of at least 5 to complete. This is a crossover study, and all subjects will be randomized to one of 2 unique sequences of lens wear.

Study Duration	
Total study duration including the enrollment period is anticipated to be approximately 6 weeks. The expected duration of participation of the subject will be approximately 1 week.

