5. TEST ARTICLE ALLOCATION AND MASKING

5.1. Test Article Allocation

The study lenses will be worn bilaterally in a randomized fashion using a 2×2 crossover design.

A computer-generated randomization scheme will be used to randomly assign subjects to one of two unique sequences of lens wear (AO1DfA/DT1fA or DT1fA/AO1DfA) using an allocation ratio of 1:1 between lens sequences.

The randomized assignment of subjects will be performed at the first visit prior to the first fitting. The Clinical site will follow the randomization scheme provided and will not pre-select or assign subjects. The following must have occurred prior to randomization:

- Informed consent must have been obtained
- The subject must have met all inclusion and exclusion criteria
- The subject history and baseline information must have been collected

[REDACTED]

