14.3. Analysis Populations

Intention-to-Treat (ITT) Population:

Intention-to-treat population will include all randomized subjects. Subjects will be analyzed as per planned randomized treatment.

Safety Population:

All subjects who are administered any study intervention. Subjects will be analyzed as per actual treatment received.

Per-Protocol Population:

All subjects who successfully complete all visits and do not substantially deviate from the protocol as determined by the trial cohort review committee prior to database hard lock. Justification for the exclusion of subjects with protocol deviations from the per-protocol population set will be documented in a memo to file.

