15.2. Subject Record

At a minimum, subject record should be available for the following:

- subject identification
- eligibility
- study identification
- study discussion
- provision of and date of informed consent
- visit dates
- results of safety and efficacy parameters as required by the protocol
- a record of all adverse events
- follow-up of adverse events
- medical history and concomitant medication
- test article receipt/dispensing/return records
- date of study completion

**Clinical Study Protocol
Johnson & Johnson Vision Care, Inc.**

- reason for early discontinuation of test article or withdrawal from the study, if applicable

The subject record is the eCRF or an external record. The author of an entry in the subject record must be identifiable. The first point of entry is considered to be the source record.

Adverse event notes must be reviewed and initialed by the Investigator.

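### Withdrawing a subject for poor vision, comfort or fit at Visit 1 means the second lens is never measured, so missing second-lens data depend partly on the primary outcome (minor)

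*Combined protocol and SAP*

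**What the plan says.** Section 8.2 lists the reasons for which a subject is withdrawn, in mandatory wording. One is "Subject not successfully dispensed due to lack of efficacy and safety including poor vision, poor comfort or unacceptable fit". Safety has bullets of its own in the same list: significant or serious adverse events, corneal infiltrative events, and the investigator's "clinical judgment regarding the subject safety reasons (that it is in the best interest of the subject to stop treatment").

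For a discontinued subject, 8.2 tells the investigator to finish the visit in progress and then to "Complete the Final Evaluation, indicating the reason that the subject was discontinued from the study". It provides for no later study visit. Section 15.2 also keeps the "reason for early discontinuation of test article or withdrawal from the study, if applicable" in the subject record. Sections 4.3 and 8.2 allow replacement, in 4.3 at the sponsor's discretion.

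The design is non-dispensing (4.1), with subjects randomised "using an allocation ratio of 1:1 between lens sequences" (5.1). The synopsis places the second lens at the second visit only: "Visit 2: Continuance, lens fit #2, Exit evaluation". Section 6.3 uses the word dispensed for in-office wear.

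For analysis, 14.3 defines the per-protocol set as "All subjects who successfully complete all visits and do not substantially deviate from the protocol", and 8.1 counts as completers only those who "have not withdrawn/discontinued from the study for any reason described in section" (the section number is lost in the public text; 8.2 is evidently meant). Sections 14.5 and 14.6 use observed cases without imputation, summarise every efficacy endpoint in both ITT and per-protocol sets, and require missing counts in each table. Sections 2.3 and 14.4 rule out hypothesis testing.

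**The concern.** A rule that stops a subject who cannot be sent home in a lens suits a dispensing study. Here nobody takes a lens home, and a washout of 1 to 10 days separates the two lenses. Poor acuity or comfort with the first lens is therefore a result to report rather than a reason to withhold the second.

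Applied at Visit 1, the rule has two effects. The second-lens value is missing for a reason linked to the primary endpoint, and the per-protocol set loses subjects who did badly. The link is partial, since comfort and fit trigger the rule as well as vision.

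At stake is how two columns of descriptive statistics read in a study of about 7 subjects. In the per-protocol set both lens columns would look somewhat too good. In ITT, where the Visit 1 acuity was recorded, the two columns would rest on different subjects.

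**Working it through.** **1. Can the rule operate?** The label non-dispensing (4.1) suggests inert template text. But 6.3 speaks of dispensing for in-office wear, so a failed fitting at Visit 1 meets the bullet. The visible text contains no exception.

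**2. What is lost?** Visit 1 is completed, so Visit 1 acuity should normally exist. Lens 2 is fitted only at Visit 2, which does not take place. The subject contributes one lens to observed-case ITT and nothing to per-protocol.

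**3. Completer count.** The plan gives no sample-size formula: 7 enrolled, at least 5 to complete, on feasibility grounds (4.3, 14.2). The implied allowance is 1 − 5/7 = 28.6%, or two subjects. Let *w* be the rate of non-safety Visit 1 withdrawal and *a* other attrition. Both are assumed, as the documents give neither. Completers are taken as Binomial(7, *c*) with *c* = (1 − *a*)(1 − *w*), without replacement.

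| *w* | Expected lost to this rule (7*w*, *a* = 0) | P(≥5 of 7), *a* = 0 | P(≥5 of 7), *a* = 10% |
|---|---|---|---|
| 0 | 0 | 1.000 | 0.974 |
| 5% | 0.35 | 0.996 | 0.932 |
| 10% | 0.70 | 0.974 | 0.869 |
| 20% | 1.40 | 0.852 | 0.692 |
| 30% | 2.10 | 0.647 | 0.487 |

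Example, *w* = 10%, *a* = 0: 21(0.9⁵)(0.1²) + 7(0.9⁶)(0.1) + 0.9⁷ = 0.124 + 0.372 + 0.478 = 0.974.

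**4. Shift in the summaries.** Simulation assumptions: 7 subjects, sequences split 3/4 or 4/3, no true lens difference, one normal acuity value per subject and lens with SD 1, between-lens correlation ρ, and the subject with the worst Visit 1 reading withdrawn. Results in SD units, averaged over which lens fails:

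| Quantity | ρ = 0.3 | ρ = 0.5 | ρ = 0.8 |
|---|---|---|---|
| (a) Per-protocol improvement, failed lens | 0.213 | 0.216 | 0.222 |
| (b) Per-protocol improvement, other lens | 0.081 | 0.122 | 0.184 |
| (c) ITT observed-case gap, failed minus other | 0.235 | 0.232 | 0.228 |
| (d) Part of (c) due to the poor reading itself, (c) − (b) | 0.154 | 0.110 | 0.044 |
| (e) Per-protocol gap, (c) − (a) | 0.022 | 0.016 | 0.006 |

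Improvement means the full-data mean minus the mean of the remaining six. The missing second-lens value contributes (b) to the ITT gap. The per-protocol gap is largest, 0.052 SD, when one conditions on which lens failed; the ITT gap then runs from 0.214 to 0.263 SD.

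Algebraic check: for either lens, the full mean minus the mean of the other six equals (withdrawn value − mean of the other six)/7. A shift of 0.216 SD thus puts the withdrawn subject 7 × 0.216 = 1.5 SD from the rest, plausible for the worst of seven.

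**5. In logMAR**, with an assumed SD of 0.05–0.15 and 0.02 logMAR per letter:

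- Failed lens, per-protocol: 0.213 × 0.05 = 0.011 to 0.222 × 0.15 = 0.033 (0.5–1.7 letters).
- Other lens, per-protocol: 0.081 × 0.05 = 0.004 to 0.184 × 0.15 = 0.028 (0.2–1.4 letters).
- ITT gap: 0.228 × 0.05 = 0.011 to 0.235 × 0.15 = 0.035 (0.6–1.8 letters).
- Largest per-protocol gap: 0.052 × 0.15 = 0.008 (under 0.4 letter).

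**The case against.** **Existing safeguards.** The reason for discontinuation is recorded, missing values are counted in every table, ITT is shown beside per-protocol, and two of the 7 places are already an allowance for loss. This stands: a loss would be visible and the count could be repaired by replacement. Neither restores the lost pair, and any replacement who completes under the same rule has passed the first fitting.

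**No value on either lens?** A reader might infer that a withdrawn subject contributes no acuity at all. The documents do not support that. Section 8.2 requires the visit in progress to be finished, so Visit 1 acuity should normally be there.

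**Clinical choice and withheld text.** Declining to continue with a subject who cannot be fitted acceptably is defensible, especially when each lens is deliberately rotated by 90° or 180° and filmed for 5 minutes (2.2.1). Section 7, with the visit procedures, is not in the public text. Refit attempts, the continuance criteria at Visit 2 and the order of acuity and fit decision may be settled there. This limits certainty and means the wording must let unsafe procedures be omitted. It does not explain why a poor fit with one lens should cancel a different lens at a later visit.

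**Materiality.** No test or between-lens estimate is planned, and the sample size was justified by the tracking software. The simulation always withdraws the worst acuity, although comfort and fit also trigger the rule, and uses one value per subject although acuity is monocular. These points stand and keep the matter minor.

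**Conclusion.** The point holds in conditional form and is minor. If the bullet is applied at Visit 1, the second lens goes unmeasured for a reason partly tied to the primary outcome, and the subject drops out of per-protocol. If nobody is withdrawn this way, the effect is zero.

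Under the stated assumptions, one such withdrawal flatters the per-protocol means by at most 0.033 logMAR. It opens an observed-case ITT gap of at most 0.035 logMAR on average, only part of which comes from the missing value. A reader might infer that the comparison of the lenses is seriously biased. The figures do not support that: the per-protocol contrast moves by under 0.4 letter, and no formal comparison is planned. Nor do the documents show that the target of 5 completers is in danger, since they give no withdrawal rate and allow replacement.

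The acuity SD, the between-lens correlation and the trigger are assumptions. Confidence is medium because Section 7 cannot be seen.

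**What to change.** Replace the 8.2 bullet with wording such as: *A poor result with the Visit 1 lens in vision, comfort or fit does not by itself lead to withdrawal. The subject attends Visit 2 unless the investigator judges, under the safety criteria above, that lens wear should stop. Visit 1 procedures that cannot safely be done with that lens (for example intentional misalignment) are omitted and recorded as missing.*

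The separate safety bullets stay as they are, and so does the per-protocol definition in 14.3. No new analysis is needed in 14.6. A table of fitting failures built from the discontinuation reason would miss the subjects who now continue, because they would have no such reason. The missing counts required by 14.5 are enough, with a footnote to the acuity table identifying any Visit 1 fitting failure from the visit records. The sponsor should check the wording against Section 7, including that those records show a failed fit.

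The cost is one reworded bullet and, if needed, one footnote. The downside is that a subject who did poorly with one lens attends one more in-office visit.
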